At each visit, including the Final Visit and the Post-Treatment Follow Up, the subject's medical history will be reviewed and any changes from baseline will be recorded on the adverse event eCRF.

If a subject reports taking any over-the-counter or prescription medications, vitamins and/or herbal supplements or if administration of any medication becomes necessary

beginning with Screening through the end of the study, the name of the medication, dosage information including dose, route and frequency, date(s) of administration including start and end dates, and reason for use must be recorded on the appropriate eCRF.

Vital Signs

Vital signs include body temperature (oral or tympanic), weight, blood pressure and pulse. On days when venetoclax is administered in the clinic, blood pressure and pulse rate will be measured after the subject has been sitting for at least 5 minutes.

NOTE: Starting with visit Week 8 Day 1, vital signs may be performed within 72 hours before or after the scheduled visit.

Physical Examination

At Screening, the subject should have a **complete physical examination**, including height and weight (height only performed during Screening). A complete physical examination should include the evaluation of head, eyes, ears, nose and throat (HEENT); cardiovascular, dermatological, musculoskeletal, respiratory, gastrointestinal and neurological systems.

A **symptom directed physical examination** may be performed at all other visits (other than screening) and should be limited to systems of primary relevance: cardiovascular, respiratory, and those associated with symptoms.

Physical Examination (Disease Assessment)

Physical examinations performed as a part of Disease Assessments (Screening, Weeks 24, 36, 48) are to include the evaluation of the presence and degree of enlarged lymph nodes in two dimension (cervical, supraclavicular, axillary, inguinal and femoral nodes), hepatomegaly, and splenomegaly. These lymph node evaluations should be noted on all physical examinations irrespective of being present or absent. Refer to Disease

Assessments (2008 Modified IWCLL NCI-WG Criteria) for additional information pertaining to methods of measurement.

Changes from baseline abnormalities should be recorded at each subsequent physical examination. New or worsened abnormalities should be recorded as AEs if appropriate.

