For all subjects, clinical response will be assessed by the Investigator at Week 24, Week 36 and Week 48. Disease response will be based on the analysis of clinical laboratory tests and a disease assessment physical examination. To confirm the response, a contrast-enhanced CT scan (or MRI, if CT scan with contrast is medically contraindicated) will be performed at Week 48 for all subjects. Subjects will be evaluated using the 2008 Modified IWCLL NCI-WG criteria for Tumor Response with the addition of CT imaging (or MRI).

For determination of CR, the CT scan and bone marrow are required to be negative, per the IWCLL NCI-WG criteria. It is recommended that the CT scan is performed first; if it does confirm a clinical response, then a bone marrow biopsy will be obtained. If a CT scan is performed and does not confirm a clinical response, a bone marrow biopsy should not be obtained.

If a subject exhibits clinical signs of possible disease progression (i.e., increased or *de novo* enlargement of liver, spleen or lymph nodes on physical examination) without an increase in lymphocytes meeting the progression of disease criteria, then additional assessments including contrast-enhanced CT scan and/or bone marrow can be performed to confirm or rule out disease progression

The same method of assessment and the same technique should be used to characterize each identified and reported lesion at baseline and during follow-up.

For any subject who has not experienced progressive disease (PD) at the time of permanent discontinuation of venetoclax, follow up phone calls will continue until death, discontinuation from the study or upon study completion.

Response criteria definitions are outlined in 2008 Modified IWCLL-WG Criteria for Tumor Response. See [Table 5](#).

NOTE: Disease assessments may be performed approximately 7 days prior to the scheduled visit.

For patients with Partial Remission at Week 48 an additional CT scan and a bone marrow examination can be done between Week 48 and Week 108 to confirm CR if there is a possibility that a patient achieved Complete Remission based on laboratory tests and a disease assessment physical examination.

Computed Tomography Scans (or Magnetic Resonance Imaging)

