Time to progression (TTP) will be defined as the number of days from the date of first dose or enrollment if not dosed to the date of earliest disease progression. All disease progression will be included regardless whether the event occurred while the subject was taking the study drug or had previously discontinued the study drug. If the subject does not experience disease progression, then the data will be censored at the date of last available disease assessment. Data for subjects who receive non-protocol, CLL therapy prior to disease progression will be censored at the last disease assessment prior to receiving non-protocol therapy. Data for subjects without any disease assessments performed after the baseline visit will be censored at the time of enrollment plus 1 day. TTP will be analyzed by Kaplan-Meier methodology using data for all subjects enrolled. Median time TTP will be calculated and 95% confidence interval for median time TTP will be presented.

Progression-free survival (PFS) will be defined as the number of days from the date of first dose to the date of earliest disease progression or death. All disease progression will be included regardless whether the event occurred while the subject was taking the study drug or had previously discontinued the study drug. If the subject does not experience disease progression or death, then the data will be censored at the date of last disease

assessment. Data for subjects who receive non-protocol, CLL therapy prior to disease progression will be censored at the last disease assessment prior to receiving non-protocol therapy. Data for subjects without any disease assessments performed after the baseline visit will be censored at the time of enrollment plus 1 day. PFS will be analyzed by Kaplan-Meier methodology using data for all subjects enrolled. Median time PFS will be calculated and 95% confidence interval for median time PFS will be presented.

Overall survival (OS) will be defined as number of days from the date of first dose to the date of death for all dosed subjects. For subjects who did not die, their data will be censored at the date of last study visit or the last known date to be alive, whichever is later. OS will be analyzed by Kaplan-Meier methodology using data from all enrolled subjects. Median time survival will be estimated and 95% confidence interval for the median time survival will be presented.

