6.2 Treatment Days

Definition of Treatment Days (Days Relative to the First Dose of Venetoclax)

Treatment (Rx) days are calculated for each time point relative to the first dose date of venetoclax. They are defined as the number of days between the day of the first dose of venetoclax and the specific time point. Rx days are negative values when the time point of interest is prior to the first venetoclax dose day. Rx days are positive values when the time point of interest is after the first venetoclax dose day. The day of the first dose of

venetoclax is defined as Rx Day 1, while the day prior to the first venetoclax dose is defined as Rx Day –1 (there is no Rx Day 0).

Definition of Final Observation

The final observation (Final Visit) is defined as the last non-missing observation collected within 30 days following the last dose of venetoclax, unless otherwise specified.

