Time to progression for a given subject will be defined as the number of days from the date the subject started venetoclax to the date of earliest PD (radiographic or clinical) (i.e., TTP = PD/censoring date – first dose date + 1 day). All PD will be included regardless of whether the event occurred while the subject was taking venetoclax or had previously discontinued venetoclax. If the subject does not experience PD, then the subject's data will be censored at the date of the last available disease evaluation or at the cut-off date for the interim analysis if the subject has a disease evaluation that is after the cut-off date. If a subject does not have any post baseline disease assessments, the data will be censored at the first dose date plus 1 day. The distribution of the time to progression will be estimated using Kaplan-Meier methodology. Median time to progression and the corresponding 95% confidence interval will be estimated.

Progression Free Survival (PFS)

Progression-free survival (PFS) will be defined as the number of days from the date of first dose of venetoclax to the date of earliest PD (radiographic or clinical) or death (i.e., PFS = PD/death/censoring date – first dose date + 1 day). All disease progression will be included regardless of whether the event occurred while the subject was taking venetoclax or had previously discontinued the study drug. If the subject does not experience disease progression or death, then the subject's data will be censored at the

date of the last available disease evaluation, last known alive date, or at the cut-off date for the interim analysis if the subjects has a disease evaluation or death that is after the cut-off date. If a subject does not have any post baseline tumor assessment or clinical assessment for progression, the data will be censored at the date of first dose plus 1 day. Progression-free survival will be analyzed by Kaplan-Meier methodology. Median duration of PFS will be calculated and 95% confidence interval for median duration of PFS will be presented.

Overall Survival (OS)

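### Read literally, the PFS no-assessment rule censors deaths that have no post-baseline assessment, so early deaths can drop out of PFS while OS counts them

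*SAP*

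**What the plan says.** **Event.** SAP 10.1.2 measures PFS from first dose to the earlier of progression and death, and death appears in the formula: "PFS = PD/death/censoring date – first dose date + 1 day". Protocol 8.1.2.2 and the synopsis use the same event.

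**General censoring rule (SAP).** This is limited to event-free subjects. It opens "If the subject does not experience disease progression or death, then the subject's data will be censored at the" and then lists the possible dates.

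**No-assessment rule (SAP).** The next sentence concerns a subject without "any post baseline tumor assessment or clinical assessment for progression, the data will be censored at the date of first dose plus 1 day". The limit to event-free subjects is not repeated.

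**No-assessment rule (protocol).** Section 8.1.2.2 says: "Data for subjects without any disease assessments performed after the baseline visit will be censored at the time of enrollment plus 1 day". Here too there is no condition on death. Both documents have a similar rule for TTP, where it does no harm because death is not a TTP event.

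**Assessment schedule.** Protocol 5.3.1.1: "For all subjects, clinical response will be assessed by the Investigator at Week 24, Week 36 and Week 48". The node, liver and spleen evaluation belongs to the same visits: "Physical examinations performed as a part of Disease Assessments (Screening, Weeks 24, 36, 48) are to include the evaluation".

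**OS.** SAP 10.1.2 counts all deaths, on or off treatment, with no assessment requirement.

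Neither document says which sentence prevails when a subject dies without a post-baseline assessment. The missing-data rules in SAP 6.4 deal with missing dates and do not settle it.

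**The concern.** The no-assessment sentence contradicts the PFS definition in its own paragraph. Programmed as it stands, it turns a death without any post-baseline assessment from an event into a censored time of 2 days. The subjects affected are those who die early, so the censoring is informative and acts in one direction only: it raises PFS.

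Two outputs are exposed. The first is the overall Kaplan-Meier PFS curve and its median. The second is the set of PFS plots planned in SAP 10.3 by 17p deletion, TP53 mutation and prior BCRi treatment, where unequal numbers of early unassessed deaths would distort the comparison. A PFS curve above the OS curve would also be hard to defend, since PFS counts every death plus progressions.

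The protocol's anchor adds a smaller fault. Section 8.1 defines enrollment as the date on which the IRT supplied a subject number, and section 5.5.3 allocates numbers at Screening, which may be up to 28 days before dosing. PFS starts at first dose, so enrollment plus 1 day can fall before time zero.

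**Working it through.** The plan states no PFS rate, so there is no PFS figure to reproduce. Its sample size of 177 is for the quality-of-life endpoint. It reproduces as (20.5 × 3.2415 / 5)² = 176.6, rounded up to 177, and does not depend on the PFS rule.

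**Dates.**
- SAP 6.2 sets the numbering of the first dose day: "venetoclax is defined as Rx Day 1". First dose plus 1 day is therefore Rx Day 2, and the SAP formula gives a PFS time of 1 + 1 = 2 days.
- Week 24 Day 1 is 23 × 7 + 1 = Day 162, which matches the nominal day in SAP Table 2.

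**Set-up.** N = 200 dosed (Protocol 8.2, SAP 4.3). Let d be the deaths before Week 24 with no post-baseline assessment, and p the progressions first recorded at Week 24. Both are assumptions. No other censoring occurs before Week 24.

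**Formulas.**
- Rule as written: the d subjects leave at Day 2 without an event. PFS = 1 just before Week 24, and 1 − p/(200 − d) at Week 24.
- Deaths kept as events: PFS = 1 − d/200 just before Week 24, and 1 − (d + p)/200 at Week 24.
- OS = 1 − d/200 at both times.

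**Just before Week 24 (Day 161), no progression yet.**

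| d | PFS as written | PFS with deaths kept | OS |
|---|---|---|---|
| 2 | 100% | 99.0% | 99.0% |
| 4 | 100% | 98.0% | 98.0% |
| 10 | 100% | 95.0% | 95.0% |
| 20 | 100% | 90.0% | 90.0% |

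**At Week 24 (Day 162).**

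| d | p | PFS as written | PFS with deaths kept | OS |
|---|---|---|---|---|
| 4 | 2 | 99.0% | 97.0% | 98.0% |
| 4 | 8 | 95.9% | 94.0% | 98.0% |
| 10 | 8 | 95.8% | 91.0% | 95.0% |
| 10 | 20 | 89.5% | 85.0% | 95.0% |

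**When PFS lies above OS at Week 24.** This needs p/(200 − d) < d/200, that is p < d(200 − d)/200: fewer than 3.92 progressions for d = 4, 9.5 for d = 10 and 18 for d = 20. With more progressions PFS falls below OS again but stays too high.

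**Later in the curve.** From Week 24 on, both versions have the same subjects at risk and the same events. Their ratio therefore stays at 200/(200 − d): 1.02 for d = 4 and 1.05 for d = 10. If the median is reached, the rule as written places it where the correct curve stands at 0.5 × (200 − d)/200, which is 49.0% for d = 4 and 47.5% for d = 10. If neither curve reaches 50%, the reported median is the same.

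**If only some early deaths are unassessed.** With 10 early deaths of which 5 have no assessment, the rule as written gives 1 − 5/195 = 97.4% at Day 161, against a correct 95.0%. If all 10 have an assessment, there is no error.

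**The case against.** **The sentence can be read as nested.** In the SAP it directly follows the rule for subjects with neither progression nor death, so it could mean only: which date to use when such a subject has no assessment. A careful programmer might take it that way. That reading is possible but not stated. In the protocol it is weaker, because a sentence on non-protocol therapy, with its own condition, stands between the two.

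**Not every early death is unassessed.** A reader might infer that all deaths before Week 24 are lost. The documents do not support that. The SAP trigger includes a clinical assessment for progression, a term it does not define. Appendix D schedules physical examination and haematology on Day 1 of Weeks 1 to 5 and at Weeks 8, 12, 16 and 20. Protocol 5.3.2.3 counts a lymphocyte rise and CLL-attributable cytopenia as progression, and 5.3.1.1 allows unscheduled CT or marrow on clinical signs. If routine visits qualify, few deaths meet the rule. The protocol's wording, which refers to disease assessments, leaves less room for this. The point stands as a limit on size.

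**Early progressions are not lost.** A reader might also infer that they are. A documented progression implies an assessment, so the rule does not reach it.

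**PFS above OS concerns curves, not subjects.** It can happen to the Kaplan-Meier estimates, mainly before Week 24. No subject's recorded PFS time is made longer; it is cut to 2 days.

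**The stakes are limited.** The synopsis calls the analyses descriptive, SAP 10.4 makes no multiplicity adjustment, and PFS is reported as a median with Kaplan-Meier plots rather than landmark rates. Early deaths remain visible in OS. All of this stands and lowers the severity, but it does not make the rule right.

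**Conclusion.** The wording is wrong as it stands in both documents and should be fixed. Followed literally, it removes from PFS any death with no post-baseline assessment, biases the Kaplan-Meier estimate upward, and allows it to lie above OS early in the curve. The Day 2 date is the SAP's; the protocol uses enrollment plus 1 day.

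The size cannot be settled from the documents, which give no early death rate for this trial and do not define a clinical assessment for progression. With 4 or 10 of 200 subjects dying unassessed before Week 24 and no progression, the error just before Week 24 is 2 or 5 percentage points. With 10 such deaths and 20 progressions at Week 24 it is 4.5 points (89.5% against 85.0%). These are upper bounds for those death counts, because they treat every early death as unassessed.

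A reader might conclude that the trial's main result is at risk. It is not: the primary quality-of-life endpoint, the sample size and OS do not use this rule, and the PFS median may not change. Severity: should-fix.

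**What to change.** In the PFS paragraphs of SAP 10.1.2 and Protocol 8.1.2.2, replace the no-assessment sentence with: *A death is a PFS event on the date of death whether or not a post-baseline assessment exists; only subjects with no death and no post-baseline assessment are censored at first dose plus 1 day.*

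This also moves the protocol's anchor from enrollment to first dose, in line with the SAP. SAP 5.1.1 analyses dosed subjects only, so a first-dose date always exists. It would help to state in the SAP which records count as a clinical assessment for progression.

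The cost is one sentence in each document, plus the definition. No data collection changes. Reported PFS becomes slightly less favourable.

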4.5 Timing of Quality of life and Efficacy Analyses and Safety Evaluations

Table 1. Summary of Analyses with Cutoff Dates and Data Included

Reason	Database Version	Cutoff Date	QoL/Efficacy Data Included	Safety Data Included
DMC	A	24 Apr 2017	Not included	All safety data ^a
DMC	F	03 Nov 2017	Not included	All safety data ^a
DMC	G	30 Apr 2018	Included	All safety data ^a

a. Safety population is defined in Section 5.1.1.

Quality of life, efficacy, and safety analysis occur when all subjects participating in the study have completed the 48-week disease assessment or have discontinued venetoclax (including early termination of the study). Quality of life, efficacy, and safety data up to the cutoff date specified in Table 1 will be considered. During this data collection period, active subjects continue to receive venetoclax, as applicable. When data collection is complete and all data management quality assurance (QA) and quality control (QC) procedures are performed, the clinical database data should be extracted for documentation and statistical analyses. The study will be considered completed when the last enrolled subject discontinues or completes the dosing regimen.

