6.4 Missing Data Imputation

Subjects with missing disease progression date, missing death date, or missing last known alive date will be considered as censored subjects for time to progression, progression free survival analysis, and survival analysis. And the subject will be censored at the interim data cutoff date.

If a respondent answers at least 50% of the items in quality of life measures, the missing items will be imputed with the average score of the answered items in the same scale. In cases where the respondent did not answer at least 50% of the items, the score for that domain will be considered missing.

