Overall survival (time to death) for a given subject will be defined as the number of days from the date the subject started venetoclax to the date of the subject's death (i.e., $OS = \text{death/censoring date} - \text{first dose date} + 1 \text{ day}$). All events of death will be included, regardless of whether the event occurred while the subject was still taking venetoclax, or after the subject discontinued venetoclax. If a subject has not died, then the data will be censored at the date of the last study visit, the last contact date, the date the subject was last known to be alive, or at the cut-off date for the interim analysis if the subject has a death that is after the cut-off date. The date of the last study visit will be determined by selecting the last available date of the following study procedures for a subject: tumor assessment, clinical disease progression, physical examination, vital signs assessment, clinical laboratory collection, study drug, adverse event and concomitant medication assessment, performance status, quality of life evaluation, survival form, and drug and study completion form. The distribution of the time to death will be estimated using Kaplan-Meier methodology. Median survival time and the corresponding 95% confidence interval will be estimated.

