10.2 Quality of Life and Efficacy Analyses

Data collected at any point prior to the specified interim cutoff date during the study will be used in the analyses, unless otherwise specified. The population of these analyses is defined in Subsection [5.1.1](#).

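### The SAP's overall-survival rule applies the data cut-off only to subjects who die after it; read literally, it biases the Kaplan-Meier OS estimate modestly upward

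*SAP*

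**What the plan says.** The OS paragraph of SAP 10.1.2 says that for a subject who has not died "the data will be censored at the date of the last study visit, the last contact date", or the date last known alive, "or at the cut-off date for the interim analysis if the subject has a death that is after the cut-off date". The cut-off appears nowhere else in that paragraph, and the list of dates has no order of priority.

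The neighbouring endpoints are wider. DOR and TTP move a subject to the cut-off when a disease evaluation falls after it. PFS does so "if the subjects has a disease evaluation or death that is after the cut-off date".

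Other passages also bear on OS:

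- SAP 10.2: "Data collected at any point prior to the specified interim cutoff date during the study will be used in the analyses, unless otherwise specified".
- SAP 4.5: "Quality of life, efficacy, and safety data up to the cutoff date specified in Table 1 will be considered". Protocol 8.1.3 sets the same limit.
- SAP 6.4, for a missing death or last-known-alive date: "And the subject will be censored at the interim data cutoff date".
- Protocol 8.1.2.2: survivors are "censored at the date of last study visit or the last known date to be alive, whichever is later", with no cut-off clause.

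**The concern.** Kaplan-Meier estimation needs the censoring date not to depend on what happens to the subject afterwards. The OS sentence makes it depend on exactly that. Of two subjects alive at the cut-off, the one who later dies is stopped at the cut-off, while the one who is later seen alive may be followed to that later contact. The period after the cut-off then contributes time at risk but no deaths.

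Records after the cut-off are to be expected. Active subjects stay on treatment while data are collected, and off-treatment follow-up runs for 2 years. The OS clause itself presupposes that such records can be in the extract. OS is a named secondary objective, and as the SAP stands two programmers could reasonably implement the rule differently.

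**Working it through.** The documents give no OS rate, event count or median, so there is no figure of the plan's own to reproduce. The check compares the wording and then sizes the effect under stated assumptions.

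**1. Triggers for censoring at the cut-off (SAP 10.1.2)**

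| Endpoint | Later disease evaluation | Later death | Later visit or contact of a living subject |
|---|---|---|---|
| DOR, TTP | yes | not named | only if a disease evaluation |
| PFS | yes | yes | only if a disease evaluation |
| OS | no | yes | no |

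**2. Hand check of the literal reading**

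At time t the estimated hazard is the true hazard h times the share of the risk set that has not yet passed the cut-off. Assume uniform accrual over A years, with the last subject reaching Week 48 (48/52 = 0.92 years) at the cut-off. If all later survivor follow-up is kept, the share lost at t is (t − 0.92)/A. The cumulative hazard missed by 18 months is therefore about h × (1.5 − 0.92)²/(2A).

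- A = 1.5: 0.3364/3 = 0.112h. For h = 0.10, S(1.5) = exp(−0.15) = 0.8607, and the bias is 0.8607 × (exp(0.0112) − 1) = 0.0097, or about +1.0 point.
- A = 1.0: 0.3364/2 = 0.168h. For h = 0.20, S(1.5) = exp(−0.30) = 0.7408, and the bias is 0.7408 × (exp(0.0336) − 1) = 0.0253, or about +2.5 points.

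These are approximate ceilings, because real follow-up stops at the last contact before extraction.

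**3. Simulation**

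From the protocol, with the schedule simplified: contacts every 4 weeks to Week 48, every 12 weeks after that, and every 26 weeks off treatment. Assumed: constant hazard of 0.05, 0.10 or 0.20 per year; accrual over 1.5 or 1.0 years; 20% per year stopping treatment; extraction 3, 6 or 12 months after the cut-off. Runs used 1 to 2 million subjects, so the error shown is almost entirely bias.

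Bias in OS at 18 months, in percentage points, with 1.5-year accrual (range over the three lags):

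| Hazard (true OS) | Literal reading | All truncated, no later information, deaths since last contact unknown | Truncated, all deaths to cut-off known, clause kept | Same, clause deleted | Proposed rule |
|---|---|---|---|---|---|
| 0.05 (92.77%) | +0.14 to +0.52 | −0.03 to +0.01 | −0.46 to −0.39 | −0.47 to −0.41 | −0.07 to +0.01 |
| 0.10 (86.07%) | +0.35 to +0.86 | −0.06 to +0.03 | −0.77 to −0.74 | −0.85 to −0.76 | −0.06 to 0.00 |
| 0.20 (74.08%) | +0.54 to +1.50 | −0.03 to +0.02 | −1.29 to −1.04 | −1.36 to −1.31 | −0.13 to +0.03 |

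With 1.0-year accrual the literal reading gives +0.3 to +2.3. Truncation with all deaths known gives −0.8 to −2.5 with the clause and −0.9 to −2.7 without it. At 12 months the literal reading is essentially unbiased. The hand ceilings of 1.0 and 2.5 agree with the simulated maxima of 0.86 and 2.3 for the same hazards and accrual.

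A further case truncates all data, censors known later deaths at the cut-off and leaves deaths since last contact unknown. With 1.5-year accrual its bias is −0.03 to +0.26.

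**4. What drives the sign**

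The upward bias comes from the one-sided trigger. The downward bias has another source: survivors are censored at a contact up to 12 weeks (on treatment after Week 48) or 6 months (off treatment) before the cut-off, while every death in that gap is counted. Deleting the clause makes it slightly worse, because censoring a later death at the cut-off is correct: that subject was alive then.

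**The case against.** The strongest objection is that SAP 4.5 and 10.2 and protocol 8.1.3 already confine efficacy data to the period up to the cut-off. On that reading survivors' later contacts and later deaths are both outside the analysis, the OS clause has nothing to act on, and the bias is about nil if deaths since last contact are also unknown. This stands. A reader might infer from the one-sided wording that OS is biased however the sentence is read, or that the clause causes any downward bias. The documents and the figures support neither. Nor is the sentence the only OS censoring rule, given SAP 6.4 and protocol 8.1.2.2.

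The objection does not dispose of the point. SAP 10.2 allows for exceptions specified elsewhere, and the OS sentence is specific to its endpoint. The no-bias reading turns that sentence into dead text. It also needs deaths since last contact to be unknown, which is doubtful on study: protocol 6.1.3.1 requires prompt reporting of deaths not attributed solely to CLL progression, and 6.1.6 requires serious adverse events within 24 hours.

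It is also fair to say that the sizes rest on assumptions and that OS is descriptive. Both stand. Larger 24-month figures can be produced, up to about +3 points with 18-month accrual, but only about (0.92 + 1.5 − 2.0)/1.5 = 28% of subjects could have 24 months of follow-up at the cut-off, so little weight belongs there.

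**Conclusion.** The OS wording is defective. It names the cut-off for later deaths only, and read literally it overstates Kaplan-Meier OS by roughly 0.1 to 2.3 points at 18 months, with essentially no effect at 12 months. That range covers hazards of 0.05 to 0.20 per year, accrual over 1.0 or 1.5 years and an extraction lag of 3 to 12 months; the documents give none of these.

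If all data are truncated at the cut-off, the clause is harmless. What remains then depends on how deaths between last contact and cut-off are handled: about nil if they are unknown, and 0.4 to 2.5 points too low if they are all known. That shortfall belongs to last-contact censoring. It should not be read as evidence against the clause, nor the whole finding as proof that OS is biased under every reading.

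Severity is minor. OS is a descriptive secondary endpoint in a single-arm study, with no hypothesis, comparator or decision threshold attached.

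**What to change.** In SAP 10.1.2, replace the last clause of the OS censoring sentence with:

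> Any subject with a death, visit or contact after the cut-off date is censored at the cut-off date; every other subject not known to have died on or before the cut-off is censored at the latest date known alive on or before the cut-off.

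Add that records after the cut-off are used only to establish that the subject was alive at the cut-off, as an explicit exception to SAP 4.5 and 10.2. Without that statement the new rule would conflict with both sections. Asking for the latest known-alive date also restores the priority that the protocol gives and the SAP list omits.

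In the simulations this rule keeps the 18-month bias between −0.13 and +0.03 points with 1.5-year accrual, and within about 0.3 points in runs with somewhat different mortality, lag and discontinuation assumptions. The largest residual is at the 3-month lag, when some 6-monthly calls have not yet fallen due. The cost is a sentence or two in the SAP and a small programming change, with no new data collection.
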